### **5. Analysis Sets**

The following analysis sets are defined: Randomization Analysis Set (Part A), Enrolled Analysis Set (Part B), Full Analysis Set (FAS), Per-Protocol (PP) Set for Immunogenicity (PPIS), Per-Protocol Immunogenicity Subset – Pre-booster SARS-CoV-2 Negative (PPIS-Neg), Safety Set, and Solicited Safety Set.

#### **5.1. Randomization Analysis Set (Part A)**

The Randomization Analysis Set consists of all participants who are randomized. Participants will be included in the treatment group to which they were randomized. Randomization Analysis Set is applicable to Part A only.

#### **5.2. Enrolled Analysis Set (Part B)**

The Enrolled Analysis Set consists of all enrolled participants. Participants will be included in the treatment group to which they were enrolled. Enrolled Analysis Set is applicable to Part B only.

### **5.3. Full Analysis Set (FAS)**

The FAS consists of all randomized/enrolled (Part A: randomized, Part B: enrolled) participants who receive one dose of IP. Participants will be included in the treatment group to which they were randomized/enrolled.

### **5.4. Per-Protocol (PP) Immunogenicity Set (PPIS)**

The PPIS consists of all participants in the FAS who receive the planned dose of IP, have pre-booster and Day 29 neutralizing antibody data against prototype virus strain, have no previous HIV infection and who have no major protocol deviations that impact key or critical data. Participants will be included in the treatment group to which they were randomized/enrolled. The PPIS will be used as the sensitivity analysis set for analyses of immunogenicity.

### **5.5. Per-Protocol Immunogenicity Set – Pre-booster SARS-CoV-2 Negative (PPIS-Neg)**

The PPIS-Neg consists of participants who are in PPIS and are pre-booster SARS-CoV-2 negative, defined as no virologic or serologic evidence of SARS-CoV-2 infection on or before booster, i.e., RT-PCR result is not positive if available at pre-booster and a negative bAb specific to SARS-CoV-2 nucleocapsid on or before booster. The PPIS-Neg will be used as the analysis set for the primary analyses of immunogenicity.

### **5.6. Safety Set**

The Safety Set consists of all randomized/enrolled (Part A: randomized, Part B: enrolled) participants who receive one dose of IP. The Safety Analysis Set will be used for all analyses of safety except for the solicited ARs. Participants will be included in the treatment group corresponding to the IP that they actually received.

### **5.7. Solicited Safety Set**

The Solicited Safety Set consists of all participants in the Safety Set who contribute any solicited AR data. The Solicited Safety Set will be used for the analyses of solicited ARs. Participants will be included in the treatment group corresponding to the IP that they actually received.

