### **7.3.1. Use of Electronic Diaries**

At the time of consent, the participants must confirm they will be willing to complete an eDiary using either an application downloaded to their smartphone or using a device that will be provided at the time of enrollment. Before enrollment on Day 1, the participant will be instructed to download the eDiary application or will be provided an eDiary device to record solicited ARs ([Section 7.4.3](#)) on Day 1.

On Day 1 (vaccination day), participants will be instructed on thermometer usage to measure body temperature, ruler usage to measure injection site erythema and swelling/induration

(hardness), and self-assessment for localized axillary swelling or tenderness on the same side as the injection arm.

On Day 1 (vaccination day), participants will record data into the eDiary starting approximately 30 minutes after the injection under supervision of the study site staff to ensure successful entry of assessments. The study site staff will perform any retraining as necessary. Participants will continue to record data in the eDiary after they leave the study site, preferably in the evening and at the same time each day, on the day of injection and for 6 days following injection.

Participants will record the following data in the eDiary:

- Solicited local and systemic reactogenicity ARs, as defined in [Section 7.4.3](#), that occur on the day of vaccination and during the 7 days after vaccination (ie, the day of injection and 6 subsequent days). Any solicited AR that is ongoing beyond Day 7 will be reported in the eDiary until it has resolved, and not to exceed 28 days after vaccination. Adverse reactions recorded in the eDiary beyond Day 7 should be reviewed by the study site staff either during the next scheduled telephone call or at the next study site visit.
- Daily oral body temperature measurement should be performed at approximately the same time each day using the thermometer provided by the study site. If body temperature is taken more than once in a given day, only the highest temperature reading should be recorded.
- Other measurements, as applicable, for solicited local ARs (injection site erythema and swelling/induration) will be performed using the ruler provided by the study site.
- Any medications taken to treat or prevent pain or fever on Day 1 or for the next 6 days.

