The eDiary will be the only source document allowed for solicited systemic or local ARs (including body temperature measurements). Participants will be instructed to complete eDiary entries daily. The participant will have a limited window on the following day to complete assessments for the previous day; quantitative temperature recordings and measurement of any injection site erythema or swelling/induration reported on the following day may be excluded from the analyses of solicited ARs.

Any new safety information reported during safety telephone calls or at site visits (including a solicited AR) that is not already captured in the eDiary will be described in the source documents as a verbally reported event. Any AR reported in this manner must be described as an unsolicited event and therefore entered on the AE eCRF.

Study site staff will review eDiary data with participants during the safety call 7 days after vaccination.

The eDiary will also be used every 2 weeks from Day 36 to Day 162 and from Day 202 to Day 342 to capture the occurrence of MAAEs, AESIs, SAEs, or AEs leading to withdrawal. The eDiary will prompt the participant to complete an eDiary questionnaire that collects the following data:

- Changes in health since last completing the questionnaire or since in contact with the study site
- Known exposure to someone with known COVID-19 or SARS-CoV-2 infection
- Any experience of symptoms of COVID-19
- Any MAAEs, AESIs, or SAEs

If an eDiary record results in identification of relevant safety events according to the study period or of symptoms of COVID-19, a follow-up safety call will be triggered.

Apart from the safety telephone calls described in [Section 7.3.2](#) at Day 8 and every 2 weeks starting from Day 43 to Day 169 and from Day 209 to Day 349, each participant will complete a questionnaire in an eDiary for Day 36 to Day 162 and from Day 202 to Day 342 ([Table 8](#)). The eDiary responses will be reviewed by study site personnel and may result in a follow-up safety call by the site to the participant.

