#### **Events NOT Meeting the Adverse Event Definition**

- Procedures planned before study entry (eg, hospitalization for preplanned surgical procedure).
- Medical or surgical procedure (eg, endoscopy, appendectomy): the condition that leads to the procedure should be the AE.
- Situations in which an untoward medical occurrence did not occur (social and/or convenience admission to a hospital).

An AR is any AE for which there is a reasonable possibility that the vaccine caused the AE ([Section 7.4.3](#)). For the purposes of investigational new drug safety reporting, “reasonable possibility” means that there is evidence to suggest a causal relationship between the vaccine and the AE.

An unsolicited AE is any AE reported by the participant that is not specified as a solicited AR in the protocol or is specified as a solicited AR but starts outside the protocol-defined period for reporting solicited ARs (ie, 7 days after vaccination).

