## 6. Statistical Analysis

### 6.1. General Considerations

Please refer to Table 8 in the protocol for Schedule of Events (SoE).

The following follow-up periods for safety analyses and Concomitant Medications will be used:

- Overall follow-up period (throughout the study): from the day of the IP injection (Day 1) to the earliest date of (study completion, discontinuation from the study, or death)
- Up to 28 days follow-up period: from the day of the IP injection (Day 1) to the earliest date of (the day of the IP injection and 27 subsequent days, discontinuation from the study, or death)
- After 28 days follow-up period: from the 28 days after the IP injection to the earliest date of (study completion, discontinuation from the study, or death)
- 7-day follow-up period: from the day of the IP injection (Day 1) to the earliest date of (Day 7 after the IP injection, discontinuation from the study, or death)

**Continuous variables** will be summarized using the following descriptive summary statistics: the number of subjects (n), mean, standard deviation (SD), median, minimum (min), and maximum (max).

**Categorical variables** will be summarized using counts and percentages.

**Baseline value**, unless specified otherwise, is defined as the most recent non-missing measurement (scheduled or unscheduled) collected before the dose of IP in this study.

For the summary statistics of all numerical variables unless otherwise specified, the display precision will follow programming standards. Please see [Appendix A](#) for variable display standards.

When count data are presented, the percentage will be suppressed when the count is zero in order to draw attention to the non-zero counts. A row denoted “Missing” will be included in count tabulations where specified on the shells to account for dropouts and missing values. The denominator for all percentages will be the number of subjects in the treatment group within the analysis set of interest, unless otherwise specified.

**End of Study** (EoS) for the participants is defined as any of completion of the study if the participant has completed all phases of the study including the last scheduled procedure as shown in the SoE (Table 8 in the protocol), discontinuation of study due to any reason, death, and termination of the trial by the Sponsor.

**Pre-booster SARS-CoV-2 status** is determined by using virologic and serologic evidence of SARS-CoV-2 infection on or before Day 1 (pre-booster).

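### Blank diary days stay in the solicited-reaction denominators, and in-window reactions reported verbally are moved to unsolicited AEs; both can only lower the solicited rates, by an amount the documents do not allow one to estimate.

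*SAP*

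**What the plan says.** **Entry to the set.** SAP 5.7: "The Solicited Safety Set consists of all participants in the Safety Set who contribute any solicited AR data". No minimum number of diary days is required. Protocol 7.3.1 has all participants start at the site: "participants will record data into the eDiary starting approximately 30 minutes after the injection under supervision of the study site staff".

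**Denominator.** SAP 6.1: "The denominator for all percentages will be the number of subjects in the treatment group within the analysis set of interest, unless otherwise specified". SAP 6.3.2 plans tables of solicited reactions over the 7-day period and by day of reporting, Day 1 to Day 7, and gives no different denominator. SAP 6.1 leaves missing data unimputed apart from listed exceptions, none of which concerns diary days. It allows a row for missing values in tables whose shells call for one.

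**Reactions reported outside the diary.** Protocol 7.3.1 makes the eDiary the sole source document for solicited reactions. For a reaction first mentioned on a call or at a visit it says: "Any AR reported in this manner must be described as an unsolicited event and therefore entered on the AE eCRF". Protocol 7.4.1 and the Glossary define an unsolicited AE as one that is not a listed reaction, or one that "is specified as a solicited AR but starts outside the protocol-defined period for reporting solicited ARs (ie, 7 days after vaccination"). Protocol 7.4.3 also provides a solicited AR eCRF page for reactions that lead to a healthcare visit or withdrawal, last beyond 7 days, or meet the SAE definition. SAP 6.3.2 accepts some solicited reactions from that page without saying which, and commits to a listing that shows the maximum grade across the two sources.

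**Next-day entries.** Protocol 7.3.1 says that temperature, erythema and swelling measurements "reported on the following day may be excluded from the analyses of solicited ARs". Neither document says when, or who decides.

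**The concern.** Frequency and grade of solicited reactions is the first-listed primary safety endpoint in both parts, and the study is meant to inform dose selection. A participant who makes the supervised entry and then stops is counted in every denominator but can reach no numerator for Days 2 to 7. The tables would not separate that person from someone who completed the diary and had no reaction.

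The routing rule is a separate matter. The Day 8 call, at which staff go through the diary with the participant, is the contact most likely to uncover an unlogged reaction. Under Protocol 7.3.1 such a reaction leaves the solicited tables and enters the unsolicited ones. It also changes scale: solicited reactions are graded automatically on Protocol Table 5 and all are taken as related (7.4.3), whereas unsolicited AEs get a mild, moderate or severe rating and a causality judgement from the investigator (7.4.8, 7.4.9).

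**Working it through.** The documents give no diary-completion rate and no expected reaction rate, so there is no planned figure to reproduce. The group size is consistent: 6 × 70 = 420 and 2 × 70 = 140. With 70 per group, one lost reactor moves a rate by 1/70 = 1.4 points.

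**1. Blank days, 7-day table.** Let p be the true 7-day rate, m the share of a group with only the supervised entry, and e the share of reactors already recorded at that entry. All three are assumptions. With the whole set as denominator:

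reported rate = p × (1 − m × (1 − e))

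| p | e | m = 2% | m = 5% | m = 10% | m = 20% |
|---|---|---|---|---|---|
| 80% | 0 | 78.4% | 76.0% | 72.0% | 64.0% |
| 80% | 0.5 | 79.2% | 78.0% | 76.0% | 72.0% |
| 50% | 0 | 49.0% | 47.5% | 45.0% | 40.0% |
| 10% | 0 | 9.8% | 9.5% | 9.0% | 8.0% |

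With m = 0 the reported rate equals p. For p = 80%, m = 10%, e = 0 and n = 70, the expected count is 0.72 × 70 = 50.4. Rounded, that is 50/70 = 71.4% (95% Clopper-Pearson 59.4% to 81.6%). Among the 63 with later entries it is 50/63 = 79.4% (67.3% to 88.5%), if blanks are unrelated to reactions.

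**2. Blank days, by-day tables.** If the true rate on a day is q and a share d of the group has no entry that day, the reported rate is q × (1 − d). For q = 50% and d = 10% this is 0.50 × 0.90 = 45.0%. Dividing by those with an entry gives 0.45 / 0.90 = 50%, again if blanks are unrelated to reactions. A reaction logged on another day does not repair a by-day figure, whereas it does secure a place in the 7-day numerator. This is why the by-day tables are the more exposed.

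**3. Verbal reports.** If a share r of reactors report only by phone or at a visit, the solicited rate is p × (1 − r). For p = 80% and r = 2%, 5% and 10%, this gives 78.4%, 76.0% and 72.0%. At r = 10% and n = 70, 56 × 0.10 = 5.6 participants per group would move to the unsolicited tables.

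**4. Which rule applies to a verbal report?** Take a headache on Day 3, gone by Day 5, not logged, and mentioned on Day 8.
- Protocol 7.3.1: unsolicited.
- Protocol 7.4.1 and Glossary: not unsolicited, because it is a listed reaction that began within the window.
- Protocol 7.4.3: none of the four triggers for the solicited AR page is met.
- SAP 6.3.2: silent, because the occasions on which that page is used are not defined.

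SAP Section 1 lets the SAP prevail where methods differ, but the SAP states no competing rule here.

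**The case against.** The strongest reply is that no passage says a blank day means no reaction. SAP 6.1 permits another denominator where one is specified, and the table shells, which are not in the documents, may add a row for missing values. That stands as a limit on the claim: the problem is the arithmetic effect of a default where the SAP is silent. A missing-value row alone would show the blanks and leave the percentage unchanged.

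The protocol also works against missing entries, with a supervised first entry, retraining, a next-day catch-up window and the Day 8 review. Blank shares may therefore be small. At p = 80% and m = 5% the shortfall is 4.0 points, against an interval about 22 points wide at n = 70 (59.4% to 81.6%). This is fair, but sampling error is symmetric in intent and this loss runs one way.

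Verbally reported reactions are not lost either: they keep a severity rating and a causality assessment and appear in the unsolicited tables. The solicited AR page catches some of them. That is true, but they are absent from the endpoint they belong to and are on a different scale.

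The next-day exclusion is permissive and covers only three measurements, and a participant with any other logged reaction stays in the numerator for any reaction. That also stands; it is a minor gap in specification.

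Finally, the inclusive set is defensible for the 7-day table. Requiring an entry after the first would drop someone who logged a real reaction at 30 minutes.

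**Conclusion.** Two points hold. First, as written, blank diary days remain in the 7-day and by-day denominators and can only lower the solicited percentages. With assumed rates of 10% to 80%, 2% to 20% of participants with only the first entry, and no reaction captured at that entry, the shortfall runs from 0.2 to 16.0 points. For the 80% case it halves if half of reactors are captured at the first entry, and it is zero if diaries are complete. Second, the rule in Protocol 7.3.1 for verbal reports contradicts the protocol's definition of an unsolicited AE, whatever the completion rate.

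A reader might infer more than the documents support:
- That the plan declares blank days reaction-free. It does not; it leaves them unaddressed.
- That reactogenicity will be understated by a known amount. The size rests on shares that the documents do not give.
- That the loss rises with dose because unwell participants skip entries. This is possible, but nothing in the documents shows it.
- That every lost solicited reaction reappears as an unsolicited AE. Only verbally reported reactions do; blank days and excluded next-day measurements do not.

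**What to change.** 1. **SAP 6.3.2, by-day tables.** Use participants with an eDiary entry on that day as the denominator, and report diary completion by arm and day.
2. **SAP 6.3.2, 7-day table.** Keep the Solicited Safety Set as defined. Add a sensitivity analysis limited to participants with an entry after the 30-minute one or with any reaction recorded. This version leans slightly upward. With p = 80%, m = 10% and e = 0.5 it gives 0.76 / (0.90 + 0.10 × 0.80 × 0.5) = 0.76 / 0.94 = 80.9%, against 76.0% from the full set. The two figures bracket the true rate if blanks are unrelated to reactions. If reactors skip more entries, both may be low, and for that reason the completion table is needed too.
3. **Routing.** Reconcile the verbal-report rule in Protocol 7.3.1 with the Glossary, 7.4.1, 7.4.3 and SAP 6.3.2, and state when the solicited AR page is used. Beside the eDiary-only row, add an all-source row (eDiary plus eCRF) that counts listed reactions with onset on Days 1 to 7. Collect onset and Table 5 detail when the reaction is reported, since regrading later is unreliable.
4. **Next-day measurements.** Flag them and show results with and without them.

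The cost is SAP wording, a protocol clarification, an eCRF completion note and a few table rows. By-day denominators become slightly smaller and the reported rates somewhat less favourable.

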## 6. Statistical Analysis

### 6.1. General Considerations

Please refer to Table 8 in the protocol for Schedule of Events (SoE).

The following follow-up periods for safety analyses and Concomitant Medications will be used:

- Overall follow-up period (throughout the study): from the day of the IP injection (Day 1) to the earliest date of (study completion, discontinuation from the study, or death)
- Up to 28 days follow-up period: from the day of the IP injection (Day 1) to the earliest date of (the day of the IP injection and 27 subsequent days, discontinuation from the study, or death)
- After 28 days follow-up period: from the 28 days after the IP injection to the earliest date of (study completion, discontinuation from the study, or death)
- 7-day follow-up period: from the day of the IP injection (Day 1) to the earliest date of (Day 7 after the IP injection, discontinuation from the study, or death)

**Continuous variables** will be summarized using the following descriptive summary statistics: the number of subjects (n), mean, standard deviation (SD), median, minimum (min), and maximum (max).

**Categorical variables** will be summarized using counts and percentages.

**Baseline value**, unless specified otherwise, is defined as the most recent non-missing measurement (scheduled or unscheduled) collected before the dose of IP in this study.

For the summary statistics of all numerical variables unless otherwise specified, the display precision will follow programming standards. Please see [Appendix A](#) for variable display standards.

When count data are presented, the percentage will be suppressed when the count is zero in order to draw attention to the non-zero counts. A row denoted “Missing” will be included in count tabulations where specified on the shells to account for dropouts and missing values. The denominator for all percentages will be the number of subjects in the treatment group within the analysis set of interest, unless otherwise specified.

**End of Study** (EoS) for the participants is defined as any of completion of the study if the participant has completed all phases of the study including the last scheduled procedure as shown in the SoE (Table 8 in the protocol), discontinuation of study due to any reason, death, and termination of the trial by the Sponsor.

**Pre-booster SARS-CoV-2 status** is determined by using virologic and serologic evidence of SARS-CoV-2 infection on or before Day 1 (pre-booster).

Positive SARS-CoV-2 status at pre-booster baseline is defined as a positive RT-PCR test for SARS-CoV-2, and/or a positive serology test based on bAb specific to SARS-CoV-2 nucleocapsid on or before Day 1.

Negative SARS-CoV-2 status at pre-booster baseline is defined as a negative RT-PCR test for SARS-CoV-2 and a negative serology test based on bAb specific to SARS-CoV-2 nucleocapsid on or before Day 1.

**Study day relative to the injection** will be calculated as below:

- a) study day prior to the injection will be calculated as: date of assessment/event – date of the injection
- b) study day on or after the date of the injection will be calculated as: date of assessment/event – date of the injection + 1

**For calculation regarding antibody levels/titers**, antibody values reported as below the lower limit of quantification (LLOQ) will be replaced by  $0.5 \times \text{LLOQ}$ . Values that are greater than the upper limit of quantification (ULOQ) will be converted to the ULOQ if actual values are not available. Missing results will not be imputed.

**Unscheduled visits:** Unscheduled visit measurements will be included in the analyses as follows:

- In scheduled visit windows per specified visit windowing rules
- In the derivation of baseline/last on-treatment measurements
- In the derivation of maximum/minimum on-treatment values and maximum/minimum change from baseline values for safety analyses
- In individual subject data listings

**Visit window rules:** The analysis visit windows for protocol-defined visits are provided in [Appendix B](#).

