- 2) Pre-booster

Seroresponse based on pre-vaccination is defined as  $\geq$  4\*LLOQ for subjects with negative SARS-CoV-2 status at their pre-vaccination baseline. For this study, subjects SARS-CoV-2 status at pre-booster baseline will be used to impute their SARS-CoV-2 status pre-vaccination baseline. If the participant tests negative at pre-booster, the serum Ab value of the pre-vaccination baseline will be imputed with LLOQ, otherwise, For subjects with positive SARS-CoV-2 status at pre-booster, their seroresponse based on pre-vaccination baseline will be set to missing.

The SRR at Day 29 will be summarized for each treatment group with its 95% CI calculated with the Clopper-Pearson method. The difference of SRRs at Day 29 for mRNA-1283 at each dose level, mRNA-1283.211 at each dose level compared with mRNA-1273 will be provided with its 95% CI with the Miettinen-Nurminen method.

Part B:

Similar analysis methods will be used to analyze immunogenicity data for Part B. An ANCOVA model will be used to compare immune response between treatment group (██████████ mRNA-1283.529). Day 29 antibody titers against B.1.1.529 will be included in the model as a dependent variable and treatment group variable (mRNA-1283.529 at each dose level) will be included as fixed effect, adjusting for age group (< 56,  $\geq$  56) and the pre-booster baseline Ab value. The GMT will be estimated by the GLSM from the model for each group and corresponding 95% CI will be provided. The ratio of GMTs for CCI mRNA-1283.529 with respect to CCI mRNA-1283.529 booster dose will be estimated by the ratio of GLSM from the model. The 95% CI for the ratio of GLSM will be provided to assess the between-group difference in immune response against B.1.1.529.

SRR against B.1.1.529 at Day 29 will be summarized for each mRNA-1283.529 dose level with its 95% CI calculated using the Clopper-Pearson method. The difference of SRRs at Day 29 between two dose levels will also be calculated with 95% CI using the Miettinen-Nurminen method.

For Part B, seroresponse will be based on both pre-vaccination and pre-booster baseline as well. The derivation rule is the same as described in Part A.

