#### **6.4.3. Analysis for the Secondary and Exploratory Immunogenicity Objectives**

Part A and B:

Immunogenicity, including the SARS-CoV-2-specific bAb and nAb along with seroresponse rate, will be assessed at multiple time points in this study (Days 1, 15, 29, 91, 181 and 366); however, Day 29, 28 days after booster dose, is the time point of primary interest.

The following evaluations will be performed at each time point for immunogenicity.

- In relation to the immune response of each booster arm to SARS-CoV-2 prototype and viral variants, the GMT or level, GMFR and SRR will be calculated at the time points where the immune response is assessed for prototype and viral variants. For each antibody of interest, the GMT or level and GMFR with their corresponding 95% CIs at each time point will be provided. The 95% CIs will be calculated based on the t-distribution of the log-transformed values then back-transformed to the original scale for presentation. The following descriptive statistics will also be provided at each time point: number of participants (n), median, minimum, and

maximum. Additionally, reverse cumulative distribution plots and box plots of titers or levels will be generated for each antibody of interest.

- For each antibody of interest, the proportion of subjects with fold-rise  $\geq 2$ , fold-rise  $\geq 3$ , and fold-rise  $\geq 4$  from baseline at each post-injection time point will be tabulated with its 95% CI calculated using the Clopper-Pearson method.
- The SRR of each treatment group against the prototype strain and variant strains, defined as the percentage of participants achieving seroresponse against the prototype strain and variant strains, respectively, will be provided with their 95% CI calculated with the Clopper-Pearson method.
- For the exploratory objectives, to characterize cellular immunogenicity, frequency, magnitude, and phenotype of antigen-specific B- and T-cells may be analyzed; comparison of the SARS-CoV-2 genetic sequence of viral isolates with the vaccine sequence and immune responses to vaccine breakthrough isolates may be performed to evaluate the genetic and/or phenotypic relationships of isolated SARS-CoV-2 strains to the vaccine sequence.

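### SAP 6.1's default denominator is not overridden for seroresponse and fold-rise percentages, so read literally a participant with no result lowers the rate, mainly at visits other than Day 29

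*SAP*

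**What the plan says.** SAP 6.1 (General Considerations) sets one rule for every percentage: "The denominator for all percentages will be the number of subjects in the treatment group within the analysis set of interest, unless otherwise specified". The same section says of antibody values: "Missing results will not be imputed".

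The seroresponse text names interval methods but no denominator:

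- SAP 6.4.2, Day 29: "The SRR at Day 29 will be summarized for each treatment group with its 95% CI calculated with the Clopper-Pearson method". The between-arm difference "will be provided with its 95% CI with the Miettinen-Nurminen method".
- SAP 6.4.3, all time points: SRR is "defined as the percentage of participants achieving seroresponse against the prototype strain and variant strains, respectively". The proportions with at least a 2-, 3- or 4-fold rise "at each post-injection time point will be tabulated with its 95% CI calculated using the Clopper-Pearson method".
- SAP 6.4.2 also says that, for participants positive for SARS-CoV-2 before the booster, "their seroresponse based on pre-vaccination baseline will be set to missing".

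Protocol 8.5.4.2 likewise defines SRR as a percentage of participants and gives no evaluable base. Elsewhere the SAP does name a different base when it wants one: in 6.2.1 the Solicited Safety Set is expressed over the Safety Set, and screen-failure reasons over those who failed screening.

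SAP 5.4 admits a participant to the per-protocol set (PPIS) on the strength of pre-booster and Day 29 neutralizing-antibody data against the prototype strain. SAP 5.5 restricts PPIS-Neg, the primary immunogenicity set, to the pre-booster negatives within it.

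**The concern.** Membership of PPIS or PPIS-Neg guarantees two prototype neutralizing-antibody results and nothing else. It does not guarantee a sample at Day 15, 91, 181 or 366, nor a binding-antibody or variant result at any visit. If the 6.1 default governs, each absent result counts in the denominator only and so acts as a non-response, although no passage says that this is wanted.

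SRR is one of three measures for the primary (Day 29) and secondary (all time points) immunogenicity endpoints, and Protocol 3.1 says that the study will inform dose selection. Later SRRs would fall with missing samples as well as with waning. Two arms could also appear to differ only because one lost more samples. GMT and GMFR, by the formulas in SAP 6.4, average the observed values, so they would describe a different group of participants from the SRR.

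**Working it through.** The documents state no SRR and no missing rate, so there is no planned figure to reproduce. The arm size of up to 70 comes from SAP 4.2. Every missing count and response rate below is an assumption.

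**1. Which rule governs?** SAP 6.1 covers all percentages unless something else is specified. Sections 6.4.2 and 6.4.3 and Protocol 8.5.4 specify nothing else for SRR or fold-rise. The non-imputation rule concerns antibody values, not denominators. Read literally, the default applies.

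**2. Where can a result be absent within the set?**

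| Result | Can it be absent? |
|---|---|
| Day 29 prototype neutralizing antibody | No: required for PPIS |
| Day 29 variant neutralizing antibody (including B.1.1.529, the Part B primary SRR) or binding antibody | Only through an assay failure or an untested aliquot, since Day 29 prototype data exist |
| Any antibody at Days 15, 91, 181, 366 | Yes: missed visit or withdrawal (Protocol 6.2 does not replace withdrawals) |
| Pre-vaccination-based seroresponse in pre-booster positives | Always missing by rule, but these participants are not in PPIS-Neg |

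**3. Size in one arm.** With r the rate among evaluable participants and m the share missing, displayed SRR = r × (1 − m). Take a set of 60 with 12 missing (m = 12/60 = 20%) and 43 responders, with Clopper-Pearson intervals:

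- Evaluable base: 43/48 = 89.6% (77.3 to 96.5).
- Full-set base: 43/60 = 71.7% (58.6 to 82.5). Check: 0.896 × 0.80 = 0.717.

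Over a range, with a set of 70 and about 90% of evaluable participants responding:

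| Missing | Evaluable base | Full-set base |
|---|---|---|
| 4 | 59/66 = 89.4% | 59/70 = 84.3% |
| 7 | 57/63 = 90.5% | 57/70 = 81.4% |
| 14 | 50/56 = 89.3% | 50/70 = 71.4% |
| 21 | 44/49 = 89.8% | 44/70 = 62.9% |

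The drop runs from about 5 points (4 missing) to 27 points (21 missing).

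**4. Size between arms.** Take two sets of 70, one with 14 missing and the other with 4, and almost equal evaluable rates. Intervals are Miettinen-Nurminen:

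- Evaluable base: 50/56 − 59/66 = 89.3% − 89.4% = −0.1 points (−12.3 to 11.4).
- Full-set base: 50/70 − 59/70 = 71.4% − 84.3% = −12.9 points (−26.5 to 1.0).

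The whole shift comes from unequal missingness.

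**5. Values set to missing.** In a PPIS arm of 70 with 14 assumed pre-booster positive and 53 of the 56 negatives responding, the pre-vaccination-based SRR is 53/56 = 94.6% on the evaluable base and 53/70 = 75.7% on the full set. In the positive subgroup every value is missing, so the rate is undefined. The literal rule would instead give a count of zero, for which SAP 6.1 suppresses the percentage.

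**The case against.** The strongest reply is that the SAP points both ways. It does not impute missing results. Setting a seroresponse to missing serves little purpose if the participant then counts as a failure, and that instruction could itself be read as specifying otherwise. A seroresponse at a time point is undefined without a sample. The table shells are not in the documents and may carry a denominator footnote. SAP 6.4.3 also calls for the number of participants alongside the titer statistics, so a reader could see how many were sampled. Missing-as-failure is, besides, a recognised conservative convention, and the comparisons are descriptive.

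Much of this stands. An evaluable denominator was probably intended, and the absence of any hypothesis, margin or decision rule limits the consequences. It does not remove the conflict: those rules govern values, the 6.1 rule governs denominators, and a programmer following 6.1 literally would use the full set. If missing-as-failure is wanted, the SAP should say so.

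Two stronger readings are tempting. A reader might infer that the SAP has chosen to score missing participants as non-responders; no passage says so, and that result is only the arithmetic of an unmodified default. A reader might also infer that the main primary-endpoint results are compromised. The documents do not support that either: Day 29 prototype neutralizing-antibody results cannot be missing in these sets, and pre-booster positives are outside PPIS-Neg.

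**Conclusion.** The point holds as an unresolved conflict within the SAP, rated should-fix. The default denominator is not overridden for SRR or fold-rise proportions and, applied literally, lowers them by the factor (1 − m).

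- **Main reach:** Days 15, 91, 181 and 366.
- **Day 29:** prototype neutralizing-antibody SRR is unaffected; variant and binding-antibody SRRs are affected only where an assay result is absent.
- **Set-to-missing rule:** matters only for the pre-vaccination-based SRR in the optional PPIS sensitivity analyses and in infection-status subgroups.

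The size rests wholly on assumed missingness. At 20% missing, an SRR near 90% would be shown near 72%. It would be wrong to say that later SRRs would track dropout instead of waning; they would reflect both.

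**What to change.** Add to SAP 6.4.2 and 6.4.3:

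> For SRR and fold-rise proportions the denominator (N1) is the number of participants in the analysis set with a non-missing baseline and a non-missing result for that antibody, strain and time point; for the pre-vaccination-based SRR it is the number with a non-missing derived seroresponse. Participants whose seroresponse is set to missing are not in N1. N1 is displayed and is used for all Clopper-Pearson and Miettinen-Nurminen intervals.

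The cost is this short addition in two sections and an N1 column in the shells, made before outputs are produced. The small downside is that an available-case rate assumes missingness is unrelated to response. A missing-as-failure version can be added as a declared sensitivity analysis for the later visits.
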